***Version Number: 2.0***  
***March 30 2020***

## **STATEMENT OF COMPLIANCE**

The study will be carried out in accordance with Good Clinical Practice (GCP) as required by the following:

- U.S. Code of Federal Regulations applicable to clinical studies (45 CFR 46)
- 21 CFR 312
- ICH GCP E6
- Completion of Human Subjects Protection Training

**PROTOCOL SUMMARY**

**Subjects:** Non-ventilated hospitalized participants with SARS-CoV-2 infection

**Study Site:** Washington University in St Louis/ Barnes Jewish Hospital

**Study Duration:** 2 years

**Number of subjects:** 500

**Subject Participation Duration:** 6 weeks

**Description of Study Design:** Open-label block randomized study with four arms:

- Arm 1. Hydroxychloroquine alone
- Arm 2. Hydroxychloroquine *plus* azithromycin
- Arm 3. Chloroquine alone
- Arm 4. Chloroquine *plus* azithromycin

**Primary**

1. Time (hours) from randomization to recovery defined as 1) absence of fever, as defined as at least 48 hours since last temperature  $\geq 38.0^{\circ}\text{C}$  without the use of fever-reducing medications AND 2) absence of symptoms of greater than mild severity for 24 hours AND 3) not requiring supplemental oxygen beyond pre-COVID baseline AND 4) freedom from mechanical ventilation or death

**Secondary**

1. Time to resolution of fever defined as at least 48 hours since last temperature  $\geq 38.0^{\circ}\text{C}$  without the use of fever-reducing medications
2. Time to improvement in symptoms (scored as mild or absent and remained so for 24 hour)
3. Mean improvement in symptom from baseline
4. Duration of hospitalization
5. Proportion requiring supplementary oxygen (above baseline usage) at any time during follow-up
6. Duration (days) of requirement for supplementary oxygen
7. Proportion requiring ICU admission at any time during follow-up
8. Proportion requiring mechanical ventilation at any time during follow-up
9. Ventilator free days
10. All-cause mortality

## **BACKGROUND INFORMATION AND SCIENTIFIC RATIONALE**

Coronavirus disease 19 (COVID-19) is a rapidly emerging pandemic caused by severe acute respiratory syndrome coronavirus 2 (SARS CoV-2). At the time of writing, over half a million people have tested positive for the virus, approximately one sixth of those are located in the US with the numbers steadily rising. At present the overall case fatality rate is estimated between 2-7% with significant variation reported between settings. The most common symptoms are fever, a non-productive cough, malaise and shortness of breath. The rapid emergence of the syndrome globally in combination with a population that does not appear to have any previous exposures has led to a rapid utilization of healthcare resources. In many hardest hit locations this has led to rationing of healthcare, and a severe strain of healthcare workers as they struggle to provide care to a significantly increased patient caseload.

At present there are no approved drugs for the management of SARS CoV-2 although a number of trials worldwide are actively recruiting. Several candidate drugs have been identified through data derived from the SARS CoV outbreak in the early 2000s as potential candidates for treatment of SARS-CoV-2 and have limited preliminary data for their use in SARS CoV-2 infection. Both Chloroquine and hydroxychloroquine have *in vitro* activity against SARS-CoV-2 and have been used extensively in the past for management of other medical conditions including autoimmune disorders and malaria prophylaxis and treatment. However, despite the limited data on the clinical benefit of these agents many international and regional guidelines are recommending their use. Recent limited reports from China showed that chloroquine can shorten symptoms, as well as reduce viral load. In a small French study, a combination of hydroxychloroquine and azithromycin reportedly appeared to be superior to hydroxychloroquine alone however the data was generated from a very small trial.

Based on pre-clinical evidence of effectiveness and evidence of safety from long-time clinical use for other indications, we propose to perform a phase III trial of hospitalized non-ventilated participants to assess if hydroxychloroquine and chloroquine in combination with azithromycin vs each drug alone improves the time to symptom resolution.

## **STUDY AIMS/ENDPOINTS**

### **Primary**

1. Time (hours) from randomization to recovery defined as 1) absence of fever, as defined as at least 48 hours since last temperature  $\geq 38.0^{\circ}\text{C}$  without the use of fever-reducing medications AND 2) absence of symptoms of greater than mild severity for 24 hours AND 3) not requiring supplemental oxygen beyond pre-COVID baseline AND 4) freedom from mechanical ventilation or death

### **Secondary**

1. Time to resolution of fever defined as at least 48 hours since last temperature  $\geq 38.0^{\circ}\text{C}$  without the use of fever-reducing medications

2. Time to improvement in symptoms (scored as mild or absent and remained so for 24 hour)
3. Mean improvement in symptom from baseline
4. Duration of hospitalization
5. Proportion requiring supplementary oxygen (above baseline usage) at any time during follow-up
6. Duration (days) of requirement for supplementary oxygen
7. Proportion requiring ICU admission at any time during follow-up
8. Proportion requiring mechanical ventilation at any time during follow-up
9. Ventilator free days
10. All-cause mortality

### **Exploratory**

1. COVID-19 specific mortality
2. Number of patients with diagnosed cardiomyopathy
3. Number of patients with new onset arrhythmia

### **STUDY DESIGN**

This Phase III trial will utilize four treatment strategies in non-critically ill participants (not requiring ICU admission and/or mechanical ventilation) with SARS CoV-2 infection. Participants will receive hydroxychloroquine or chloroquine with or without azithromycin. The primary outcome will be time from randomization to recovery

### Enrollment

Hospitalized patients with documented SARS CoV-2 infection will be screened for study eligibility. If eligible, consenting participants will be randomized to one of the four arms. Up to 125 participants will be recruited for each of the study groups, with a planned total enrollment of 500 participants. Participants will be randomized to either one of the following arms in a 1:1:1:1 manner. Drugs will be provided by the BJC investigational pharmacy using standardized Epic order sets. If participants are discharged, we will coordinate with the investigational pharmacy services to ensure that participants receive the full course of therapy.

**Arm 1:** Hydroxychloroquine 400mg orally twice a day for one day, followed by 200mg twice a day for four consecutive days (Five days in total). The drug will be supplied in 200mg tablets.

**Arm 2:** Hydroxychloroquine 400mg orally twice a day for one day, followed by 200mg twice a day for four consecutive days (Five days in total). The drug will be supplied in 200mg tablets.  
AND

[figure not shown]
Azithromycin 500mg orally once, followed by 250mg daily for four consecutive days (five days total). The drug will be supplied in 250mg tablets.

**Arm 3:** Chloroquine phosphate 1000mg orally once, followed in 12 hours by 500mg, then 500mg orally twice daily for 4 days (Five days in total). The drug will be supplied in 500mg tablets.

**Arm 4:** Chloroquine phosphate 1000mg orally once, followed in 12 hours by 500mg, then 500mg orally twice daily for 4 days (Five days in total). The drug will be supplied in 500mg tablets.

AND

Azithromycin 500mg orally once, followed by 250mg daily for 4 consecutive days (5 days total). The drug will be supplied in 250mg tablets.

## SUBJECT INCLUSION CRITERIA

- Hospitalization for management of SARS CoV-2 infection
- Positive SARS CoV-2 test
- Age  $\geq 18$  years
- Provision of informed consent
- Electrocardiogram (ECG)  $\leq 48$  hours prior to enrollment
- Complete blood count, glucose-6 phosphate-dehydrogenase (G6PD), comprehensive metabolic panel and magnesium  $\leq 48$  hours prior to enrollment from standard of care.
- If participating in sexual activity that could lead to pregnancy, individuals of reproductive potential who can become pregnant must agree to use contraception throughout the study. At least one of the following must be used throughout the study:
  - Condom (male or female) with or without spermicide
  - Diaphragm or cervical cap with spermicide
  - Intrauterine device (IUD)
  - Hormone-based contraceptive

## SUBJECT EXCLUSION CRITERIA

- Contraindication or allergy to chloroquine, hydroxychloroquine or azithromycin
- Current use hydroxychloroquine, chloroquine or azithromycin
- Concurrent use of another investigational agent
- Invasive mechanical ventilation
- Participants who have any severe and/or uncontrolled medical conditions such as:
  - unstable angina pectoris,
  - symptomatic congestive heart failure,
  - myocardial infarction,
  - cardiac arrhythmias or know prolonged QTc  $>470$  males,  $>480$  female on ECG
  - pulmonary insufficiency,
  - epilepsy (interaction with chloroquine),
- Prior retinal eye disease
- Concurrent malignancy requiring chemotherapy
- Known Chronic Kidney disease, eGFR $<30$  or dialysis
- G-6-PD deficiency, if unknown requires G6PD testing prior to enrollment
- Known Porphyria
- Known myasthenia gravis
- Currently pregnant or planning on getting pregnant while on study
- Breast feeding
- AST/ALT  $>$  five times the upper limit of normal ULN\*
- Bilirubin  $>$  five times the ULN\*
- Magnesium  $<1.4$  mEq/L\*
- Calcium  $<8.4$  mg/dL  $>10.6$  mg/dL\*
- Potassium  $<3.5$   $>5.5$  mEq/L\*
- Current concomitant use of contraindicated drugs including antiarrhythmics, antidepressant, anticonvulsants (see Appendix 2 for full list)

\*Patients who do not meet laboratory criteria may be rescreened within 48 hrs.

## **Discontinuation criteria**

### **Discontinuation of treatment**

- Lack of efficacy, defined as deterioration of the clinical condition or delayed response requiring, in the opinion of the investigator, alternative therapy
- Occurrence of an AE that, in the opinion of the investigator, warrants discontinuation of the subject from the study drug
- Pregnancy

### **Discontinuation of study participation**

- Withdrawal of consent;
- Investigator or Sponsor decision that withdrawal is in the subject's best interest
- Lost to follow up (every attempt should be made to contact the subject). Three attempts will be made to contact participants electronically or by phone. If unsuccessful, a letter will be sent to the participant to encourage follow up. Thereafter if a response is not received in 14 days the participant will be considered lost to follow up.

## **POTENTIAL RISKS AND BENEFITS**

### **Potential risks:**

#### **Drug associated risks**

##### **Risks of chloroquine:**

The following adverse reactions have been identified during post-approval use of Chloroquine or other 4-aminoquinoline compounds. Because these reactions are reported voluntarily from a population of uncertain size, it is not always possible to reliably estimate their frequency or establish a causal relationship to drug exposure.

Ocular disorders: Maculopathy and macular degeneration have been reported and may be irreversible. Irreversible retinopathy with retinal pigmentation changes (bull's eye appearance) and visual field defects (paracentral scotomas) in patients receiving long-term or high-dosage 4-aminoquinoline therapy have been reported. Visual disturbances (blurring of vision and difficulty of focusing or accommodation); nyctalopia; scotomatous vision with field defects of paracentral, pericentral ring types, and typically temporal scotomas (e.g., difficulty in reading with words tending to disappear, seeing half an object, misty vision, and fog before the eyes) have been reported. Reversible corneal opacities have also been reported.

Immune system disorders: Urticaria, anaphylactic reaction including angioedema.

Ear and labyrinth disorders: Nerve type deafness; tinnitus, reduced hearing in patients with preexisting auditory damage.

Musculoskeletal and connective tissue-disorders: Sensorimotor disorders, skeletal muscle myopathy or neuromyopathy leading to progressive weakness and atrophy of proximal muscle groups, depression of tendon reflexes and abnormal nerve conduction.

Gastrointestinal disorders: Hepatitis increased liver enzymes, anorexia, nausea, vomiting, diarrhea, abdominal cramps.

Skin and subcutaneous tissue disorders: Erythema multiforme, Stevens-Johnson syndrome, toxic epidermal necrolysis, exfoliative dermatitis. Pleomorphic skin eruptions, skin and mucosal

Version 2.0. March 30th 2020

pigmentary changes; lichen planus-like eruptions, pruritus,; drug rash with eosinophilia and systemic symptoms (DRESS syndrome); photosensitivity and hair loss and bleaching of hair pigment.

Blood and lymphatic system disorders: Pancytopenia, aplastic anemia, reversible agranulocytosis, thrombocytopenia and neutropenia. Hemolytic anemia in G6PD deficient patients.

Nervous system disorders: Convulsions, mild and transient headache, polyneuropathy, acute extrapyramidal disorders (such as dystonia, dyskinesia, tongue protrusion, torticollis).

Neuropsychiatric disorders: Neuropsychiatric changes including psychosis, delirium, anxiety, agitation, insomnia, confusion, hallucinations, personality changes, depression, and suicidal behavior.

Cardiac disorders: Hypotension, electrocardiographic changes (particularly, inversion or depression of the T-wave with widening of the QRS complex), and cardiomyopathy (which may result in cardiac failure and in some cases a fatal outcome).

Cardiac arrhythmias, conduction disorders such as bundle branch block / atrio-ventricular block, QT interval prolongation, torsade de pointes, ventricular tachycardia and ventricular fibrillation have been reported with therapeutic doses of Chloroquine as well as with overdose. The risk is greater if Chloroquine is administered at high doses. Fatal cases have been reported.

Metabolic and Nutritional disorders: Hypoglycemia.

Risk of overdose: Chloroquine is very rapidly and completely absorbed after ingestion. Toxic doses of Chloroquine can be fatal. As little as 1 g may be fatal in children. Toxic symptoms can occur within minutes. The symptoms of overdosage may include nausea, vomiting, headache, drowsiness, visual disturbances, cardiovascular collapse, convulsions, hypokalemia, rhythm and conduction disorders including QT prolongation, torsades de pointes, ventricular tachycardia and ventricular fibrillation, followed by sudden potentially fatal respiratory and cardiac arrest. Immediate medical attention is required, as these effects may appear shortly after the overdose. Cases of extrapyramidal disorders have also been reported in the context of Chloroquine overdose.

## **Risks of hydroxychloroquine**

Rare (1% to 10%):

Vision loss due to retinopathy which may be irreversible

Frequency not defined:

Central nervous system: Ataxia, dizziness, emotional disturbance, emotional lability, headache, irritability, lassitude, nervousness, nightmares, psychosis, seizure, sensorineural hearing loss, suicidal tendencies, vertigo

Dermatologic: Acute generalized exanthematous pustulosis, alopecia, bleaching of hair, bullous rash, dyschromia (skin and mucosal; black-blue color), erythema multiforme, erythema of skin (annulare centrifugum), exacerbation of psoriasis (nonlight sensitive), exfoliative dermatitis, lichenoid eruption, maculopapular rash, morbilliform rash, pruritus, skin photosensitivity, Stevens-Johnson syndrome, toxic epidermal necrolysis, urticaria

Endocrine & metabolic: Exacerbation of porphyria, weight loss

Gastrointestinal: Anorexia, diarrhea, nausea, stomach cramps, vomiting

Hematologic & oncologic: Agranulocytosis, anemia, aplastic anemia, hemolysis (in patients with glucose-6-phosphate deficiency), leukopenia, purpuric rash, thrombocytopenia

Hepatic: Acute hepatic failure (rare), hepatic insufficiency (rare)

Hypersensitivity: Angioedema

Neuromuscular & skeletal: Myopathy (including palsy or neuromyopathy, leading to progressive weakness and atrophy of proximal muscle groups; may be associated with mild sensory changes, loss of deep tendon reflexes, and abnormal nerve conduction)

Ophthalmic: Accommodation disturbance, corneal changes (transient edema, punctate to lineal opacities, decreased sensitivity, deposits, visual disturbances, blurred vision, photophobia [reversible on discontinuation]), decreased visual acuity, macular edema, nystagmus disorder, optic disc disorder (pallor/atrophy), retinal pigment changes, retinal vascular disease (attenuation of arterioles), retinitis pigmentosa, scotoma, vision color changes, visual field defect

Otic: Tinnitus

Respiratory: Bronchospasm

<1%, postmarketing, and/or case reports: Cardiomyopathy, epithelial keratopathy (Dosso 2007), hypoglycemia (Cansu 2008; Unübol 2011), macular degeneration, maculopathy

#### **Risks of azithromycin:**

Common (>10%):

Gastrointestinal: Loose stools (≤14%; single-dose regimens tend to be associated with increased incidence), vomiting (children, single-dose regimens tend to be associated with increased incidence: 1% to 14%; adults: ≤2%; adults, single 2 g dose: 1% to 7%), diarrhea (2% to 9%; single-dose regimens 4% to 14%), nausea (≤7%; high single-dose regimens 4% to 18%)

Rare (1% to 10%):

Cardiovascular: Chest pain (≤1%), palpitations (≤1%)

Central nervous system: Dizziness (≤1%), drowsiness (≤1%), fatigue (≤1%), headache (≤1%), vertigo (≤1%)

Dermatologic: Skin rash (≤5%; single-dose regimens tend to be associated with increased incidence), dermatitis (children: ≤2%), pruritus (≤2%), skin photosensitivity (≤1%)

Endocrine & metabolic: Increased lactate dehydrogenase (1% to 3%), increased gamma-glutamyl transferase (1% to 2%), increased serum potassium (1% to 2%), decreased serum bicarbonate (adults: ≥1%), decreased serum glucose (adults: >1%)

Gastrointestinal: Abdominal pain (1% to 7%; single-dose regimens tend to be associated with increased incidence), anorexia (≤2%), dysgeusia (≤1%), dyspepsia (≤1%), flatulence (≤1%), gastritis (≤1%), melena (adults, multiple-dose regimens: ≤1%), mucositis (≤1%), oral candidiasis (≤1%)

Genitourinary: Vaginitis (≤3%), genital candidiasis (adults, multiple-dose regimens: ≤1%)

Hematologic & oncologic: Decrease in absolute neutrophil count (children: 15% to 16%; 500 to 1,500 cells/mm^3), decreased hematocrit (adults: >1%), decreased hemoglobin (adults: >1%), increased neutrophils (adults: >1%), thrombocythemia (adults: >1%), change in neutrophil count (children: ≥1%), eosinophilia (≥1%), lymphocytopenia (≥1%)

Hepatic: Increased serum ALT (≤6%), increased serum AST (≤6%), increased serum bilirubin (≤3%), cholestatic jaundice (≤1%)

Neuromuscular & skeletal: Increased creatine phosphokinase (1% to 2%)

Renal: Increased serum creatinine (≤6%), increased blood urea nitrogen (≤1%), nephritis (adults, multiple-dose regimens: ≤1%)

Respiratory: Bronchospasm (≤1%)

Miscellaneous: Fever (children: (≤2%)

Participants will be fully consented and aware of the potential risks associated with their participation in the study and have the knowledge that they can discontinue the study at any

time. Before a patient is approached, permission will be received from the treating physician. Consent will be performed by a physician co-investigator or be delegated to a coordinator under the supervision of a physician co-investigator. A physician co-investigator will review and approve all enrollments. Consents may be performed utilizing electronic informed consent as possible, but paper informed consent will be available as well. Each subject will be monitored carefully and appropriately and will be instructed to contact the study team promptly upon noticing any complication or health issues. Should this occur, subjects' health history will be reviewed by the study team.

All subjects asked to participate in the clinical studies will be advised that their participation in the studies is entirely voluntary, that they can choose discontinue participation at any time and that this will not negatively impact on their access to routine health care.

For participants enrolled under a legal authorized representative (LAR), the PI for the project, or a designated research coordinator, will maintain the enrolled subject's name and date of birth in a secured electronic format. Throughout the patient's stay, they will periodically review if the participant has recovered the ability to understand the nature of study participation and to make his/her own medical decisions. When this occurs, the enrolled subject will be provided a signed copy of the consent document that was originally signed by and provided to the LAR, informed that they were enrolled in the study, and the section regarding withdrawal of consent will be specifically pointed out to them if they choose to do that. Furthermore, they will be allowed to ask questions regarding their participation in the study and the purpose of the study from the research coordinator or PI during that encounter. For participants that are scheduled to be placed in a LTAC facility or any other facility who are still unable to consent prior to transfer, the PI or designated research coordinator will make every effort to have a second copy of the signed consent form provided to the LAR and to inform the LAR once again that the participant or the LAR can contact the PI in the future at any time as described in the consent form to discuss the study or to withdraw consent.

### **Other risks to staff and research participants**

Given the known contagious potential for COVID-19, we will take several precautions to limit risks to staff and other participants following federal, state, local and university guidelines. We will ensure that we are following WU/HRPO guidelines as they are updated.

### **Known Potential Benefits**

Preliminary data suggests that hydroxychloroquine or chloroquine used alone or in combination with azithromycin could improve outcomes in SARS CoV-2 infection.

### **RANDOMIZATION PROCEDURES**

Randomization will be performed by the BJH Investigational Drug Service (IDS) using a computer-generated randomization sequence, which will be concealed from investigators and the research team through study completion. Consented patients will be randomly assigned to one of four open-label treatment cohorts in a 1:1:1:1 ratio using permutation blocks (block size will be determined by the study statistician). Medications will be prepared and dispensed by the IDS pharmacy and delivered to the appropriate coordinator. The research pharmacy will maintain randomization, dispensing, and accountability logs. All medications will be stored in a

secure location within the research pharmacy and maintained under controlled environmental conditions.

### **Handling of Withdrawals**

Subjects are free to withdraw from the study at any time.

Subjects may be taken off study without their consent if the study doctor determines that it is in the subject's best interest not to continue to participate in the study. In addition, the study doctor may remove a subject from study participation if the subject is unable to complete the required study procedures, or if the study is stopped by the institution, the sponsor, or the Food and Drug Administration (FDA) or other health authorities. If the subject is removed from the study, the Principal Investigator or designee will contact the participant to discuss the study stopping procedures.

Participants who withdraw are withdrawn or terminated from the study, or are lost to follow-up after study enrollment visit will not be replaced.

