### Follow up

Participants will be asked to complete daily symptom surveys for 14 days from randomization, then weekly thereafter for 4 weeks resulting in a total duration of follow up of 42 days. During hospitalization, daily symptom surveys will be completed in conjunction with the study coordinators via telephone. On discharge participants will have the option to complete electronic symptom surveys or complete symptom surveys via telephone with study coordinator. In the event that the participant opts for electronic symptom surveys on discharge they will also

receive a follow up call from a study coordinator every 7 days during the initial 14 day period. In addition, failure to submit a symptom survey will prompt a study follow up call.

On discharge from hospital in addition to completing daily symptom surveys participants will be asked to take and record their temperature twice daily with extra recordings performed if concern for fever onset.

Symptoms will be collected using the Flu-PRO scale (appendix 1) validated for use in influenza as at present validated tools for COVID-19 are not available.

To assure safety and protocol adherence phone calls to participants will be initiated if there is no contact at the designated time points.

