### Reporting Requirements

Adverse events must be reported by study personnel into the Redcap system using the electronic case report forms within 3 days of their knowledge of the occurrence. Investigators are responsible for following all relevant local IRB policies and procedures. The Principal Investigator will follow IRB policy in terms of reporting adverse events.

Serious Adverse Events that occur within 6 weeks after randomization must be reported by the site investigator or personnel into the Redcap system on the Serious Adverse Event CRF within 1 working day after the site investigator or personnel first learn of the event.

For SAEs, the Principal Investigator will review the report and obtain any needed additional clarifications concerning the event by direct telephone conversations and/or e-mail with the involved providers. The investigator's description and categorization of the event, and additional relevant information, will then be reviewed by the study's Safety Officer. The Safety Officer will determine if the event was properly categorized. If not, he will provide the Principal Investigator with a modified categorization, along with a brief written rationale for re-categorizing the event. In nearly all instances, the Safety Officer's categorization will be considered the final categorization of the event.

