#### *Primary endpoint analysis*

The primary endpoint of this study is the time to recovery following the definition outlined in the STUDY AIMS/ENDPOINTS section. Our primary analysis will be to use Kaplan-Meier (KM) survival analysis to test the statistical null hypothesis that there is no difference in recovery rates between the non-AZM treatment arms and the AZM treatment arms (HCQ vs HCQ + AZM, CQ vs CQ + AZM). If either of the AZM arms have significantly faster recovery rates (two-sided  $P$ -value  $< 0.05$ ) compared to the corresponding non-AZM arm group, then we will conclude that the AZM group is superior to the non-AZM group. We will also compare recovery rates between the HCQ vs CQ, and HCQ + AZM vs CQ + AZM treatment arms to assess whether HCQ and CQ treatments differentially influence recovery. We will then proceed to a multivariable Cox-regression model that adjusts symptom severity at baseline (sum of presence of fever  $\geq 38.0^{\circ}\text{C}$  and total number of 'Quite a Bit' or 'Very much' responses to the Flu-PRO questionnaire [maximum total = 20]). The final model will retain the treatment groups and those covariates that are significant ( $P < 0.05$ ) in the multivariable model and we will report the model-adjusted hazard ratios and 95% CI for the treatment groups as well as the covariates. Participants that are lost to follow-up or die will be censored at the date of last contact or date of death, respectively, and patients that do not recover during the study period will be censored at 42 days. The primary analysis will be intention-to-treat and a per-protocol analysis will also be performed as a secondary analysis of the primary endpoint. Statistical analyses will be conducted using PROC LIFETEST and PROC PHREG as appropriate (SAS Institute Inc, Cary, NC, USA).

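### Participants can be removed from the study for being unable to complete procedures, and the plan does not say whether record-based follow-up continues or how they enter the primary analysis

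*Combined protocol and SAP*

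**What the plan says.** Handling of Withdrawals (under Randomization Procedures) provides that "the study doctor may remove a subject from study participation if the subject is unable to complete the required study procedures". The only step it describes afterwards is that "the Principal Investigator or designee will contact the participant to discuss the study stopping procedures". Participants who withdraw, are withdrawn or "are lost to follow-up after study enrollment visit will not be replaced".

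Discontinuation of study participation gives a different list of reasons for leaving: withdrawal of consent, "Investigator or Sponsor decision that withdrawal is in the subject's best interest", and loss to follow-up after a defined series of contact attempts. Inability to complete procedures is not on it. Discontinuation of treatment is a separate list, and it is the only one that mentions a worsening patient: "Lack of efficacy, defined as deterioration of the clinical condition or delayed response".

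Under Follow up, "Participants will be asked to complete daily symptom surveys for 14 days from randomization", then weekly to day 42. The Schedule of events marks medical record review at every time point to day 42, with a footnote extending it to study outcomes, AEs and SAEs. Under Reporting Requirements, "Serious Adverse Events that occur within 6 weeks after randomization must be reported", and no exception is made for removed participants.

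The Primary endpoint analysis is intention-to-treat. "Participants that are lost to follow-up or die will be censored at the date of last contact" or at the date of death, respectively, and those who have not recovered are censored at day 42. Participants removed by the study doctor are not mentioned. The Sensitivity analyses section examines censoring by death only.

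**The concern.** A patient who is intubated, delirious or very breathless may be unable to answer a daily symptom survey. The withdrawal rule allows that patient to be taken out of the study altogether, although the protocol elsewhere separates stopping study drug from leaving the study. The decision is discretionary, depends on prognosis, and is made by someone who can know the treatment.

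Two things are then undefined. The first is whether death, ventilation, ICU admission, oxygen use and SAEs are still collected, although record review could supply them without any effort from the patient. The second is whether the participant counts in the primary analysis as censored on leaving or as not recovered to day 42. Censoring on leaving treats a deteriorating patient as having the same prospect of recovery as those still followed. That raises the estimated recovery curve, and it favours whichever arm has more such removals.

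**Working it through.** **1. The plan's own figure.** Inputs from Sample size and power analysis: medians 11 and 7 days, censoring c = 0.04 per day, 125 per arm, two-sided alpha 0.05; follow-up is 42 days.
- Hazard h = ln 2 / median: 0.0630 and 0.0990 per day.
- P(recovery observed by day 42) = h/(h+c) × [1 − exp(−42(h+c))] = 0.604 and 0.710.
- Expected events = 125 × (0.604 + 0.710) = 164.2.
- Power (Schoenfeld) = Φ(½ × √164.2 × ln(11/7) − 1.96) = Φ(2.896 − 1.96) = 82.5%.

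The stated 82% reproduces, so the point concerns bias and not arithmetic.

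**2. How much censoring is not death.** With the same inputs, the share censored before recovery by day 42 is c/(h+c) × [1 − exp(−42(h+c))] = 38% (median 11) and 29% (median 7). Sensitivity analyses anticipates mortality of about 1.4%. The death-only sensitivity analysis therefore addresses a small part of the planned censoring.

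**3. Effect on absolute recovery, equal removal.** Assume that a share q deteriorates and does not recover by day 42, and that the rest have median 11 days. True recovery at day 42 is (1 − q) × [1 − exp(−0.0630 × 42)] = (1 − q) × 0.929.
- q = 15%: 0.85 × 0.929 = 79%. If every deteriorating patient in both arms is censored on day 4, the Kaplan-Meier estimate is about 93%. This is the extreme case.
- q = 10%, all removed between days 2 and 10: day-28 recovery reads 82%, against 75% if they are retained as not recovered.
- q = 1.4%: the difference at day 28 is about 1 point.

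The hazard ratio between arms stays at 1.00 in all of these.

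**4. Effect on the comparison, unequal removal.** Simulated log-rank tests with 125 per arm, median 11 days in both arms, no treatment effect, and removed patients censored on day 4. Two-sided false-positive rates, accurate to about 1 point:

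| Deteriorating | 75%/25% removed, no other censoring | 75%/25% removed, plus 0.04 per day |
|---|---|---|
| 10% | about 13% | about 8% |
| 15% | about 20% | about 10% |
| 20% | about 30% | about 13% |

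For the 15% row the apparent hazard ratios are 1.18 and 1.13. With 60%/40% removal and no other censoring, the rate is about 7% at 15% deteriorating (7 to 9% over the range 10% to 20%). At 15% with 0.04 per day added, it is about 6% (hazard ratio 1.05). Equal removal gives about 5%.

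**5. When deterioration itself differs by arm.** Suppose 10% deteriorate without azithromycin and 20% with it, and all are removed between days 2 and 10, with no other censoring.
- Median 11 days in everyone else: hazard ratio 0.95 if censored, 0.79 if retained. The azithromycin arm is found significantly slower in about 5% of runs if censored and 37% if retained.
- Medians 11 and 7 days in everyone else: hazard ratio 1.49 if censored, 1.03 if retained. Azithromycin is declared superior in 77% and 4% of runs.

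The last comparison needs no difference in how investigators apply the rule. Censoring alone can hide a difference in deterioration.

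**The case against.** The case against is substantial, and most of it limits how far the point goes.

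- A reader might infer that the plan censors removed patients at last contact. It does not say so. Loss to follow-up has its own definition (failed contact attempts, a letter, 14 days), which an inpatient removed by the doctor does not meet. Censoring at day 42 under intention-to-treat is also a possible reading. Last-contact censoring is the likely default, not a stated rule.
- A reader might infer that the removal rule contradicts the six-week SAE requirement, or that the monitoring board will undercount harm. Nothing in the removal rule ends SAE reporting or record review. Neither section says that these continue after removal, so loss of the data is possible but not prescribed.
- A reader might infer that deterioration is a reason for leaving the study. It is listed only as a reason for stopping treatment. The consent text under Potential Risks and Benefits expects some participants without capacity to remain enrolled through a representative. In hospital the survey is done with a coordinator by telephone, and a missed survey prompts a call. The removal wording is permissive.
- A reader might take 20% as the expected false-positive rate. It rests on a 75%/25% imbalance that no document supports, and it omits the plan's own censoring.

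What remains is a written ground for removal that falls mainly on the sickest, with no statement on follow-up or analysis afterwards. Intention-to-treat keeps these people in their randomized group but does not supply outcomes that were never collected.

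**Conclusion.** The point holds as a gap in the plan that should be closed before it affects data. A discretionary, open-label ground for removal is related to prognosis, does not appear in the plan's own list of reasons for leaving, and has no rule for follow-up or analysis attached.

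Its size cannot be fixed from the documents, because they give no rate of deterioration, removal or imbalance. If removed patients are censored at last contact, absolute recovery is overstated: by about 7 points at day 28 with 10% removed in both arms, and by about 1 point at 1.4%. The test of azithromycin keeps its 5% error rate if deterioration and removal are alike in the two arms, is mildly affected at 60%/40% removal, and is seriously affected only under strong imbalance or if one arm deteriorates more. In each unequal case examined, the bias favours the arm with more removals. No sensitivity analysis in the plan would reveal it.

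**What to change.** - **Handling of Withdrawals:** delete inability to complete procedures as a ground for leaving the study.
- **Handling of Withdrawals and Discontinuation of study participation:** reconcile the two lists. State that an investigator decision to stop, including one made in the participant's best interest, ends participant-facing procedures but not outcome follow-up.
- **Follow-up after stopping:** unless the participant withdraws consent to record review, continue abstracting vital status, ventilation, oxygen, ICU admission, hospital stay and SAEs to day 42. Use the record review in the Schedule of events and the SAE window in Reporting Requirements.
- **Primary endpoint analysis:** state that such participants stay in the intention-to-treat analysis, at risk as not recovered to day 42 unless recovery is documented. Deaths found by record review follow the plan's rule for deaths.
- **Sensitivity analyses:** add one that censors these participants at removal, since some may recover at home without a record of it. Report removals by arm, with reason and day.

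The cost is a few sentences in an amendment, one consent line, and continued chart abstraction for those who stop procedures. No visit is added, and decisions on study drug are untouched.
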